There are currently 2 randomised controlled trials (RCTs) comparing IF with arthroplasty for undisplaced FNF. Lu et al. found a slightly higher Harris Hip Score after 6 months and 1 year in favour of hemiarthroplasty but not thereafter. Dolatowski et al. found a faster mobility (TimedUp-And-Go) but no difference in the Harris Hip Score. These studies did not show a clinical difference in Harris Hip Scores, but this measure may not be the best primary outcome measure due to the ceiling effect and lack of validation for patients with hip fracture (Wamper et al.). Mobilisation on the other hand is perhaps the most important factor for mortality and should therefore be essential to measure in any hip fracture study (Kristensen et al.). There are other study types comparing IF with arthroplasty for undisplaced FNF and a meta-analysis from 2021 (Xu and Xue) with 750 patients concluded that hemiarthroplasty provided a lower implant-related complication rate, lower reoperation rate, superior hip function without increased long-term mortality. Two later studies found lower reoperation rate for IF but otherwise no difference in mortality or functional outcome (Mukka et al., Wolf et al.) and one study did not find any difference in reoperation, mortality or functional outcome (Cordero-Ampuero et al.).

Overall there is a lack of high quality studies with large sample sizes in order to compare IF with arthroplasty for undisplaced FNF.

Objectives

The aim of this trial is to compare functional outcomes of arthroplasty with internal fixation for patients over 65 years old with an undisplaced FNF. The study is designed as a national single-blinded pragmatic 1:1 RCT. The hypothesis states that arthroplasty is superior to internal fixation using the New Mobility Score (NMS) as the primary outcome after 12 months.

Section 3: Study Methods

Trial design

The SENSE trial is a national, pragmatic, single-blinded randomized controlled trial (RCT) conducted across 19 public hospitals in Denmark thereby covering app. 94% of the Danish population.

Randomization

Patients are randomly assigned in a 1:1 ratio to either receive arthroplasty or IF.

Randomization is conducted electronically through REDCap, using randomly varied blocks of sizes 4 and 6, stratified by hospital.

Sample size

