Mortality							X

Section 4: Statistical Principles

Confidence intervals and P values

The statistical significance level is determined to 5% (p<0.05)

No correction for multiple testing will be performed, as the study has one clearly specified main hypothesis.

The confidence intervals to be reported are 95% (95% CI)

Adherence and protocol deviations

Adherence is defined as receiving the allocated surgical procedure as per randomization. Participants will be considered adherent if they undergo the surgical procedure they were allocated to.

Adherence rates will be reported as the proportion of participants in each group who received their allocated intervention. Non-adherence, including reasons for any deviations, will be documented and categorized. Adherence to intervention will be presented as frequencies and percentages of participants adhering to intervention and participants not adhering to the intervention.

Definition of protocol deviations in the trial: Protocol deviations are defined as any deviation from the procedures described in the protocol for the study.

Description of which protocol deviations will be summarized: All deviations from protocol will be described.

Analysis population

We define the Intention-to-Treat (ITT) population includes all randomized participants analyzed according to their allocated group, regardless of the surgery performed or follow-up completion. The Per-Protocol (PP) population consists of participants who received their allocated surgical procedure without major protocol deviations. The Complete-Case population includes participants with no missing data for the primary outcome.

Section 5: Trial Population

Screening data

Screening data was not collected as part of this trial; therefore, no reporting on the representativeness of the trial sample based on screened individuals is available.

Eligibility

All patients with an undisplaced FNF classified as either Garden type I or II²¹ are evaluated. The patients are included if:

- Age ≥65 years
- Undisplaced FNF
- Posterior tilt <20°
- NMS=5 and above, indicating an ability to walk prior to the fracture
- Cognitive state intact to achieve informed consent

Patients are excluded if:

- The fracture is pathological
- The patient does not speak or understand Danish language

Recruitment

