All patients are recruited in the emergency department when diagnosed with an undisplaced FNF. The admitting doctor or a senior consultant will inform the patient about the trial while the patient is in the emergency department. The information will be given verbally as well as by written participant information in an undisturbed room in the emergency department. If no next of kin are present, they will be invited to attend by phone if requested by the participant. Otherwise, an impartial assessor can be assigned. Because surgery is required to take place as quickly as possible due to a higher risk of mortality when delaying surgery, a reflection time of only 2 hours has been approved. Retrieval of informed consent will take place at either the emergency department or the ward.

Withdrawal/follow-up

Withdrawal and loss to follow-up will be recorded throughout the study. Timing and reasons will be summarized descriptively, with frequencies by treatment group. Participants with available data will remain in the ITT analysis

Baseline patient characteristics

Baseline patient characteristics include age, sex, residency, pre-fracture mobility, comorbidity (using the American Society of Anaesthesiologists Classification), diseases, medication, smoking, and alcohol.

Section 6: Analysis

Outcome definitions (primary, secondary, and other measures)

Outcome Definitions

Primary Outcome

New Mobility Score (NMS): The NMS will be assessed at baseline (pre-fracture recall), 3, 6, and 12 months, with the 12-month assessment serving as the primary endpoint. The NMS ranges from 0 to 9.

Secondary Outcomes

Oxford Hip Score (OHS): The OHS will be assessed at baseline (pre-fracture recall), 3, 6, and 12 months. Scores range from 0 to 48, with higher scores indicating better hip function.

EuroQol 5-Dimension 5-Level (EQ-5D-5L): The EQ-5D-5L measures health-related quality of life, including mobility, self-care, usual activities, pain/discomfort, and anxiety/depression, each rated from 1 to 5. A visual analog scale (VAS) from 0 to 100 (worst to best health) is also included. The EQ-5D-5L will be assessed at baseline, 3, 6, and 12 months. Scores will include an index value derived from the EQ-5D-5L scale and a VAS score ranging from 0 to 100. EQ-5D-5L scores at 12 months are a secondary outcome.

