Verbal Rating Scale for Pain (VRS): The VRS for pain will measure patient-reported pain intensity on a scale from 0 (no pain) to 10 (worst possible pain). This outcome will be recorded at multiple time points to capture immediate and longer-term pain levels (2 weeks, 6 weeks, 3 months, 6 months, and 12 months). The Pain score is measured on a 0-10 scale. The VRS at 12 months is a secondary outcome.

Reoperation Rate: This outcome captures any surgical procedures related to implant failure or complications following the initial surgery. Reoperations will be tracked up to 12 months and will include any additional surgery required. This measure is categorical (yes/no), indicating whether a reoperation occurred within 12 months. Reoperations will be subdivided into major and minor: major is defined as any surgery that leads to the change of an implant or parts of it, removal of an implant (not simple removal of internal fixation), open reduction of a dislocated hip, operation due to periprosthetic fracture, or a DAIR (Debridement, antibiotics, and implant retention) procedure. Minor is defined as simple hardware removal of internal fixation or closed reduction of a dislocated hip.

Mortality: Mortality will be recorded as a binary outcome (alive/deceased) whenever the event occurs within the study period.

Exploratory Outcomes

These outcomes will not be included in the primary paper and consists for de Morton Mobility Index (DEMMI), Cumulated Ambulation Score, and X-ray measurements.

Analysis method

Primary Outcome Analysis

The primary outcome will be analyzed using a linear mixed-effects model to account for repeated measures across time points (baseline, 3, 6, and 12 months). The model will include fixed effects for time, and the

interaction between time and treatment, along with random intercepts for both hospital and individuals to account for within-subject correlation.

Time will be treated as a categorical variable.

$t = 0, \dots, T$ (observations time points) (fixed effect)

$i = 1, \dots, I$ (participants) (random effect as random intercept γ_i)

Treatment arm as fixed effect exposure with interaction with time

Baseline measurements will be included as time point 0.

Treatment effect at each time point

$$Y_{i,t} = b_{treatment,t} Treatment_i time_t + b_t time_t + \gamma_i + \varepsilon_{i,t}$$

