We will use an unstructured covariance structure for the random effects. If it improves model fit, time will also be added as a random effect to account for variability in NMS across time points within individuals.

Presentation: Estimated differences in NMS scores between treatment groups will be presented with β -coefficients, 95% confidence intervals (CIs), and p-values. Treatment effects will be displayed graphically across time points to illustrate trajectories by group, with error bars representing 95% CIs.

Secondary Outcome Analyses

Oxford Hip Score (OHS), EQ-5D-5L, and Verbal Rating Scale for Pain (VRS) will each be analysed using mixed-effects models as described for the primary outcome.

Reoperation Rate and Mortality: Binary outcomes (reoperation and mortality within 12 months) will be analysed using logistic regression models with treatment as a fixed effect and hospital as a random effect. Additionally, for mortality, time-to-event analysis will be conducted using Cox proportional hazards models with baseline hazards stratified by hospital.

Presentation: For secondary outcomes, results will be presented with β -coefficients, odds ratios (for binary outcomes), hazard ratios (for time-to-event mortality analysis), 95% CIs, and p-values.

[Adjustments for Covariates](#)

Analyses of the primary and secondary outcomes will be done twice, once unadjusted, and once adjusted for following covariates: Age (continuous), Sex (male/female), Comorbidity (measured by the American Society of Anesthesiologists classification).

[Assumptions Checking for Statistical Methods](#)

Linear Mixed-Effects Models: Assumptions of normality and homoscedasticity for residuals will be checked by examining quantile-quantile (Q-Q) plots and residual-vs-fitted plots.

Logistic and Cox Models: Assumptions of linearity and proportional hazards, respectively, will be assessed. The proportional hazards assumption in Cox models will be evaluated using Schoenfeld residuals. Deviations from linearity in logistic models will be reviewed by adding polynomial terms or piecewise splines as needed.

Alternative Methods if distributional assumptions do not hold

If normality assumptions are violated in the linear mixed-effects model, non-parametric bootstrapping with 1,000 replicates will be used to estimate 95% CIs for treatment effects.

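### The adjusted secondary analyses leave out pre-fracture NMS, which is already collected; adding it would be a small, nearly free gain for OHS, EQ-5D-5L, pain and mortality

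*SAP*

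**What the plan says.** SAP Section 6, Adjustments for Covariates, sets one rule for all outcomes: "Analyses of the primary and secondary outcomes will be done twice, once unadjusted, and once adjusted". The adjusted version is "adjusted for following covariates: Age (continuous), Sex (male/female), Comorbidity (measured by the American Society of Anesthesiologists classification". No reason is given for choosing these three.

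Pre-fracture NMS is available. Section 5, Eligibility, requires "NMS=5 and above, indicating an ability to walk prior to the fracture". Section 6 states "The NMS will be assessed at baseline (pre-fracture recall), 3, 6, and 12 months", and the data collection table in Section 3 shows NMS at admission. Section 5 also describes the sample by it: "Baseline patient characteristics include age, sex, residency, pre-fracture mobility, comorbidity".

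OHS, EQ-5D-5L and pain "will each be analysed using mixed-effects models as described for the primary outcome". In that model "Baseline measurements will be included as time point 0", and the formula gives treatment a coefficient at every time point from t = 0 to T. Mortality is analysed by logistic regression (hospital as random effect) and by a Cox model stratified by hospital. Mortality has no baseline value of its own.

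**The concern.** A pre-treatment value that should be known for every eligible participant, and that plausibly predicts later function and survival, is used only as the time-0 outcome in the NMS model. The other adjusted models contain no NMS, and the mortality models contain no measure of pre-fracture function at all.

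For OHS, EQ-5D-5L and pain, the time-0 score might be thought to do this job. OHS at baseline is labelled as pre-fracture recall. EQ-5D-5L and pain are not so labelled and may reflect the state with a fresh fracture. More importantly, the model as written makes little use of the time-0 score for the 12-month contrast (see the working).

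At stake are some interval width for the patient-reported outcomes, and a chance imbalance in pre-fracture function (330/2 = 165 per arm) that would stay in the adjusted results. The mixed models also rely on data being missing at random, which is easier to defend if pre-fracture function is in the model. That last benefit is not quantified here.

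**Working it through.** **The plan's own figure.** The SAP gives no precision or power for any secondary outcome. Its only sample-size figure, 127 per group for NMS, reproduces: 2 × (2.2/1)² × (1.960 + 1.645)² = 9.68 × 13.0 ≈ 125.8, so 126 by the normal formula. With the noncentral t distribution it is 127 (power 95.04%). Nothing below changes it.

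**Step 1: what own baseline contributes.** With a free treatment coefficient at each visit including time 0, the fixed part gives each arm its own mean at each visit. With complete data, the estimated 12-month coefficient is then the raw difference in 12-month means, whatever the within-person correlation. A numerical fit (participant random intercept, hospital effect omitted) confirmed this: −0.0156001750691873 against −0.0156001750691870. Own baseline therefore adds nothing to that contrast with complete data, and it enters only through participants with missing visits. If the model were instead coded with no treatment term at time 0, own baseline would be used and Step 3 would apply.

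**Step 2: OHS, EQ-5D-5L and pain, model as written.** Let r be the partial correlation of NMS with the 12-month score given the other model terms (an assumption). The SE is multiplied by √(1 − r²), and the equivalent gain in sample size is 1/(1 − r²).

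| r | SE factor | interval narrower by | equivalent n |
|---|---|---|---|
| 0.1 | 0.995 | 0.5% | 1.01 |
| 0.2 | 0.980 | 2.0% | 1.04 |
| 0.3 | 0.954 | 4.6% | 1.10 |
| 0.4 | 0.917 | 8.3% | 1.19 |

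Simulating 2,000 trials per setting with 230 completers (330 less 30%) gave SE reductions of about 1–2%, 4–5% and 7–9% for NMS–outcome correlations of 0.2, 0.3 and 0.4.

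**Step 3: the same outcomes with own baseline used efficiently.** Let r1 be the correlation of own baseline with outcome, c that of own baseline with NMS, and r2 that of NMS with outcome. The partial correlation is (r2 − r1·c)/√((1 − r1²)(1 − c²)).

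- r1 = 0.5, c = 0.5, r2 = 0.3: 0.05/0.75 = 0.067, SE factor 0.998 (0.2% narrower).
- r1 = 0.4, c = 0.5, r2 = 0.4: 0.20/√(0.84 × 0.75) = 0.252, SE factor 0.968 (3.2% narrower).

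The six combinations tried lie between these two. If own baseline were nearly unrelated to both NMS and outcome, the gain would move back towards Step 2.

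**Step 4: mortality, logistic model.** The assumptions were 330 participants, 1:1 allocation, control risk 10% or 20%, treatment odds ratio 0.5, NMS confined to 5–9 (SD 1.46), and one other risk score standing in for age and ASA. There were 1,500 simulated trials per setting.

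| Control risk | OR per point lower NMS | SE of log-OR without → with NMS | Power without → with NMS |
|---|---|---|---|
| 10% | 1.2 | 0.460 → 0.463 | 33.5% → 34.5% |
| 10% | 1.5 | 0.461 → 0.471 | 33.4% → 34.6% |
| 20% | 1.2 | 0.328 → 0.331 | 57.6% → 57.3% |
| 20% | 1.5 | 0.328 → 0.339 | 54.3% → 57.0% |

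The SE rises by about 1–4%, while the estimate moves further from zero (in the last row from −0.672 to −0.713). Any gain is therefore in power, about 0 to 3 points. A separate simulation at 8–17% mortality gave a ratio of mean non-centrality of 1.003–1.066, for example power 0.56 to 0.58. The Cox model was not simulated.

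**The case against.** The strongest objection is that this is a matter of preference. The covariate list is pre-specified and clear, and it contradicts nothing. It concerns secondary outcomes, each also reported unadjusted, and under randomisation chance imbalance adds variance, not bias. This stands, and it is why the point is minor.

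A second objection is that own baseline already covers prior function in the mixed models. It fails for the formula as written (Step 1). It does point to a more direct remedy, a common baseline mean or adjustment for own baseline. That is a separate change. It would shrink the gain from NMS without necessarily removing it.

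Third, eligibility confines NMS to 5–9, which limits its prognostic spread, so the partial correlation could be below 0.2. This also stands.

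Fourth, deaths are few. At an assumed 8–17% mortality, 330 participants give about 26 to 56 deaths. Over 19 hospitals that is about 1 to 3 per Cox stratum. One more parameter is tolerable but not free.

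A reader might also infer that the SAP itself names pre-fracture NMS as a driver of mortality, since the background says "Mobilisation on the other hand is perhaps the most important factor for mortality". The text does not support that. It speaks of mobilisation, as an argument for measuring mobility as an outcome, and cites a study of process performance measures. That pre-fracture NMS predicts death is a plausible assumption here, not a statement of the plan.

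**Conclusion.** The point holds as a minor, optional improvement. A baseline value that every eligible participant should have is left out of the adjusted secondary models. For OHS, EQ-5D-5L and pain, including it could narrow the 12-month intervals by roughly 2–8% at assumed partial correlations of 0.2–0.4. The gain is about 0.2–3% in the combinations tried with own baseline used efficiently. All these correlations are assumptions.

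For mortality, the benefit is correction of chance imbalance and about 0–3 points of power under the assumed risks and odds ratios. It would be tempting to say that the mortality interval is wider than it need be. The calculation shows the opposite for the conditional odds ratio, and the Cox hazard ratio shares the same non-collapsibility. A reader might extend the point to reoperation, but the SAP offers no link between NMS and reoperation, and no figure supports one.

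**What to change.** In SAP Section 6, Adjustments for Covariates, add pre-fracture NMS as one linear term to the adjusted models for OHS, EQ-5D-5L and pain, with its coefficient allowed to differ by visit, and to the adjusted logistic and Cox models for mortality. Leave the reoperation model and the NMS model's own handling of baseline unchanged.

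The cost is a line of wording and no new data. It adds one parameter to each mortality model, where deaths are few. In the mixed models it adds one parameter per visit: four for OHS and EQ-5D-5L, and six for pain, by the data collection table. The SAP is dated December 2024, plans the analysis for spring 2025 and keeps the analysts blinded until the analyses are final. On that timetable the change can be fixed in advance, and it should be made only while allocation is still blinded.

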The primary outcome for the study is the New Mobility Score (NMS) measured at 12 months. Based on prior studies, a clinically meaningful difference in NMS of 1 point was selected, with an expected standard deviation of 2.2 points. To achieve 95% power at a 5% significance level, 127 participants are required per group. Accounting for an anticipated 30% loss to follow-up due to mortality or other causes, the target enrolment is set at 330 participants.

Framework

This study employs a superiority framework to determine whether arthroplasty provides significantly better functional outcomes than IF. Specifically, the hypothesis is that arthroplasty will result in higher NMS scores compared to IF at 12 months post-surgery.

Interim analysis and stopping guidelines

An interim analysis will be conducted after data collection from the first 70 participants, focusing on mortality and function. If a mortality difference of 10% or an NMS difference of 2 points between groups is observed at 30 days or 3 months, respectively, the trial steering committee will review whether the trial should continue. The interim analysis did not meet the set criteria's and the steering committee recommended to continue the trial.

Timing of final analysis

The final analysis will be performed after all follow-up data, including the 12-month assessments, are collected. It is estimated that the last follow-up data is collected by February 2025. Thus, the complete analysis will be conducted in spring 2025.

Timing of outcome assessments

Assessments occur at:

Baseline:	During hospital admission with demographics, comorbidity, admission, surgery, blood samples, x-rays, NMS, Pain ratings using the Verbal Rating Scale (VRS), Oxford Hip Score (OHS), and Cumulated Ambulation Score (CAS).
2 and 6 weeks:	Pain VRS, CAS at 6 weeks
3 months:	NMS, CAS, Pain VRS, OHS, EuroQol 5-Dimension 5-Level (EQ-5D-5L), Barthel-20, and the de Morton Mobility Index (DEMMI).
6 months:	NMS, Pain VRS, OHS, EQ-5D-5L, Barthel-20, and DMMI.
12 months:	NMS (primary endpoint), Pain VRS, OHS, EQ-5D-5L, Barthel-20, DMMI, reoperation rates, and mortality.

Timeframe for collection of data

	Admission	2 weeks	6 weeks	3 months	6 months	12 months	At event
Demographics	X						
Comorbidity	X						
Admission	X						
Surgery	X						
Blood	X						
X-ray	X						X
NMS	X			X	X	X	
Pain VRS	X	X	X	X	X	X	
OHS	X			X	X	X	
EQ-5D-5L	X			X	X	X	
DEMMI	X			X	X	X	
Barthel-20	X			X	X	X	
CAS	X		X	X			
Reoperation							X
Complications							X

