If the proportional hazards assumption is violated in the Cox regression model for mortality, we will conduct a Kaplan-Meier survival analysis. The survival curves for each treatment group will be plotted, and differences between groups will be tested using the log-rank test.

Sensitivity Analyses

Intention-to-Treat vs. Per-Protocol: The primary analysis will be conducted as intention-to-treat (ITT). A sensitivity analysis will be conducted per-protocol to assess treatment effects among participants who fully adhered to assigned interventions.

Missing Data

No missing data is expected for the Cox regression outcome (mortality and reoperation rate). For all other outcomes, mixed-effects models inherently account for missing data under the assumption that it is Missing at Random (MAR). A dropout table will be presented, summarizing the number and timing of participants lost to follow-up by treatment group.

Harms

A table summarizing all recorded harms, excluding reoperations, will be presented.

Statistical Software

All statistical analyses will be performed using Stata 18.

References

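### The only effect estimate that addresses non-adherence is a per-protocol contrast that is no longer randomised; an allocation-based estimate should stand beside it

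*SAP*

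**What the plan says.** Section 6 (Sensitivity Analyses) makes ITT primary. Section 4 (Analysis population) defines ITT as "all randomized participants analyzed according to their allocated group, regardless of the surgery performed or follow-up completion".

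One sensitivity analysis follows: "A sensitivity analysis will be conducted per-protocol to assess treatment effects among participants who fully adhered to assigned interventions". Section 4 defines its population: "The Per-Protocol (PP) population consists of participants who received their allocated surgical procedure without major protocol deviations". Under Adherence and protocol deviations, the same section says: "Participants will be considered adherent if they undergo the surgical procedure they were allocated to".

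The remaining provision for non-adherence is descriptive. Adherence is reported as a proportion by arm, and "Non-adherence, including reasons for any deviations, will be documented and categorized". No other treatment-effect estimate takes account of the operation actually received.

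**The concern.** Randomisation balances the arms as allocated. Removing participants by the operation they received, which is settled after randomisation, need not remove the same kind of participant from each arm.

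The SAP's Background describes fixation as the smaller initial surgical trauma and arthroplasty as the larger. Suppose a frail participant allocated arthroplasty is given fixation instead. That participant leaves the arthroplasty arm of the per-protocol set. An equally frail participant allocated fixation receives fixation and stays. The arthroplasty arm has lost poor-prognosis participants whose counterparts remain in the fixation arm, and the contrast moves towards arthroplasty, the hypothesised direction. Other switching patterns can move it the other way.

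What is at stake is interpretation. If switching occurs, readers will ask how far it diluted the ITT effect and will look to the per-protocol result. That result mixes the removal of dilution with selection and cannot separate them.

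**Working it through.** **The plan's own figure.** Section 3 (Sample size) states that "a clinically meaningful difference in NMS of 1 point was selected, with an expected standard deviation of 2.2 points", with 95% power at 5% and 127 per group. Taking a two-sided test (sidedness is not stated), the normal approximation gives n = 2 × (1.960 + 1.645)² × 2.2² / 1² = 125.8, so 126. The t-test version gives 126.76, so 127. The figure reproduces, and 1 point and SD 2.2 serve as yardsticks below.

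**Assumed inputs (not in the SAP).** Share *a* of participants would receive fixation whatever their allocation, and share *b* would always receive arthroplasty. The rest, compliers, receive what they are allocated. On the same operation, always-fixation participants score *g* points below compliers, and always-arthroplasty participants score *h* points above them.

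**Per-protocol difference with no treatment effect.**
- Arthroplasty arm keeps compliers and always-arthroplasty: mean = b·h / (1 − a).
- Fixation arm keeps compliers and always-fixation: mean = −a·g / (1 − b).
- Difference = b·h / (1 − a) + a·g / (1 − b).

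With a = 0.10, b = 0.05, h = 0:
- g = 1.5: 0.15 / 0.95 = +0.16.
- g = 2: 0.20 / 0.95 = +0.21.

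The ITT difference is 0 in both.

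The sign is not fixed. With g = 0 and always-arthroplasty participants 2 points worse (h = −2), the difference is −0.10 / 0.90 = −0.11.

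**With a true effect of 1 point** (a = 0.10, b = 0.05, g = 1.5, h = 0.5):
- ITT = 0.85 × 1 = 0.85.
- Per-protocol: arthroplasty arm (0.85 × 1 + 0.05 × 1.5) / 0.90 = 1.03; fixation arm −0.15 / 0.95 = −0.16; difference 1.19.
- Complier effect = ITT / difference between arms in the proportion receiving arthroplasty = 0.85 / (0.90 − 0.05) = 1.00.

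**One-sided switching, checked by simulation.** If share *c* of the arthroplasty arm only is given fixation, and these participants score *g* below the rest, the bias is c·g. Results from 20,000 simulated trials with no effect and 115 per arm (330 × 0.70 / 2 = 115.5):

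| c | g | Mean per-protocol difference | Per-protocol type I error | ITT type I error |
|---|---|---|---|---|
| 5% | 2 | +0.10 | 6.4% | 5.1% |
| 10% | 1 | +0.10 | 6.4% | 5.1% |
| 10% | 2 | +0.20 | 10.5% | 5.0% |
| 15% | 2 | +0.30 | 17.4% | 4.7% |

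**Scale.** The standard error of a difference with 115 per arm is 2.2 × √(2/115) = 0.29. Biases of 0.16 and 0.21 are about 0.55 and 0.72 of one standard error.

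**Does the planned model remove the bias?** As written in Section 6, the model has a treatment term at every time point, baseline included, so the 12-month contrast is not conditioned on pre-fracture NMS. The adjusted version adds age, sex and ASA class. It would remove part of the imbalance if carried into the per-protocol analysis, which the SAP does not state.

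**The case against.** The confirmatory inference is sound. ITT is primary, it suits a pragmatic superiority trial, and per-protocol is already labelled a sensitivity analysis on which no conclusion is made to rest. A secondary per-protocol analysis is conventional. Adherence by arm, with reasons, lets readers judge dilution for themselves. The size is wholly assumed, and eligibility requires a pre-fracture NMS of 5 or more and intact cognition, so a 10% subgroup unsuited to arthroplasty is not obvious. All of this stands, and it limits the weight of the point. It does not alter the fact that the one effect estimate addressing non-adherence is exposed to selection.

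A complier analysis restricted to observed 12-month scores would bring its own selection, because Section 3 anticipates 30% loss from death or other causes. That also stands, and is why the fix below states a missing-data assumption and adds the estimate beside per-protocol.

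A reader might infer three stronger things that the SAP does not support:
- **That Sections 4 and 6 contradict each other on the population.** Section 6 names the per-protocol analysis, Section 4 defines its population, and the reference to full adherence reads naturally as shorthand for that definition. Section 4 does not say which deviations are major, only that "Protocol deviations are defined as any deviation from the procedures described in the protocol for the study". The protocol, not shown here, may grade them.
- **That fixation participants later converted to arthroplasty would be dropped, removing failures from one arm.** Section 4 ties adherence to the allocated procedure, and Section 6 treats later surgery as a separate outcome, reoperation.
- **That the per-protocol result would be uninformative.** A bias below one standard error does not support that.

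**Conclusion.** The point holds as a limitation of the sensitivity analysis; the primary result is not affected. The per-protocol contrast excludes participants on a post-randomisation event that can depend on prognosis, so it can be biased under no treatment effect. With 10% always receiving fixation and scoring 1.5 to 2 points lower, and 5% always receiving arthroplasty with average scores, the bias is about +0.16 to +0.21 NMS points, or 16% to 21% of the 1-point meaningful difference. These rates and gaps are assumptions. If switching is rare or unrelated to prognosis, the bias is small, and other patterns can reverse its sign. The change is worth making because an allocation-based estimate needs only data already collected.

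**What to change.** In Section 6 (Sensitivity Analyses), before unblinding:

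- **Add** a complier average causal effect on 12-month NMS in all randomised participants, with randomised allocation as instrument for the index operation received and hospital in the model. Handle missing 12-month NMS under the same missing-at-random assumption as the primary analysis, for example by multiple imputation using baseline, 3- and 6-month NMS.
- **Keep** per-protocol as supportive only. Define it by Section 4's adherence rule alone (allocated index operation performed), and state that later reoperation is not a reason for exclusion. Align the Section 4 population definition with this, so that no grading of deviations is needed.

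The cost is SAP wording and a short addition to the Stata code. Surgery data are collected at admission and adherence by arm is already to be reported, so no new data are needed. There are two downsides. The confidence interval is wider: with 10% and 5% switching, the standard error is roughly 0.29 / 0.85 = 0.34, treating the compliance difference as known. The estimate also relies on the exclusion restriction, that allocation affects NMS only through the operation received. This is plausible for a single operation but not certain.
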